5. GENERAL CHARACTERISTICS ANALYSES

5.1 SUBJECT DISPOSITION

The following subject data will be tabulated by treatment and overall:

- The number of screen failures
- The number and percentage of subjects who completed or discontinued the study as documented on the study termination page and the number and percentage of subjects for each study discontinuation reason
- The number of subjects in each analysis set
- The number and percentage of subjects for each analysis visit

All information collected in the eCRF concerning allocation, code breaking, study discontinuation and information on phases, dates of first signed informed consent, last visit and last contact (over the whole study) will be listed.

5.2 IMPORTANT PROTOCOL DEVIATIONS AND ELIGIBILITY

The number and percentage of subjects with important protocol deviations, per category and type, will be tabulated, by treatment and overall.

All available information concerning important protocol deviations violations on eligibility criteria (only violated eligibility criteria having DV.DVCAT = 'INCLUSION/EXCLUSION CRITERIA') and restrictions will be listed.

5.3 DEMOGRAPHIC AND OTHER BASELINE CHARACTERISTICS

5.3.1 *Available data*

The following parameters will be available:

- Demographics: women of childbearing potential (yes / no / post-menopausal), age, sex, race, BMI, height and weight at screening, date of birth, and date of signing informed consent form (ICF), smoking status, duration and number of pack-years
- Screening tests: serology (Human Immunodeficiency Virus Antibody (Ab-HIV1 and 2), Hepatitis B surface Antigen (HBsAg), Hepatitis B core antibody (anti-HBc), immunoglobulin M Hepatitis B core antibody (IgM anti-HBc), Hepatitis C Virus Antibody (Ab-HCV)) and Hepatitis C Virus RNA PCR, ethanol and urine drug screen (cannabinoids, opiates, cocaine, benzodiazepine, amphetamines and barbiturates) and cotinine test
- Baseline disease characteristics: date of diagnosis, type of diagnosis (usual interstitial pneumonia (UIP) pattern, possible UIP pattern, probable UIP pattern), IPF diagnosis confirmation, biopsy, antifibrotic treatment for IPF (Nintedanib or Pirfenidone), SoC treatment (Nintedanib or Pirfenidone) well tolerated, exacerbation history (number of exacerbations in the 3 months before screening and end date of the most recent exacerbation)

	Statistical Analysis Plan	
CLI-10067AA1-01	Final Analysis	Final 1.0 of 30MAY2024

5.3.2 *Derivation rules*

The following parameters will be derived:

- Age categories:
 - ≥ 40 and < 65 years
 - ≥ 65 and < 85 years
 - ≥ 85 years
- Time since diagnosis (years): (date of ICF – date of diagnosis)/365.25

Note: Partially missing dates will be imputed as specified in section 6.3.2

- Time since most recent exacerbation (months): (date of ICF – date of last documented acute exacerbation)/30.4375

Note: Partially missing dates will be imputed as specified in section 6.3.2

5.3.3 *Presentation of results*

Demographics will be presented by treatment and overall using descriptive statistics for age, height, weight, BMI, smoking duration and number of pack-years (current and ex-smokers only) and frequency tabulations for sex, race, age category and smoking status (tobacco and/or e-cigarettes).

Baseline disease characteristics will be presented by treatment and overall using descriptive statistics for continuous parameters and frequency tabulations for categorical parameters.

All demographic data, baseline disease characteristics and screening tests will be listed.

5.4 MEDICAL HISTORY AND CONCOMITANT DISEASES

5.4.1 *Available data*

Medical history and concomitant diseases findings are coded using the medical dictionary for regulatory activities (MedDRA, see section 10.3) into system organ classes and preferred terms. For each finding (MH.MHCAT is ‘GENERAL MEDICAL HISTORY’), a start and stop date or ongoing flag is collected.

5.4.2 *Derivation rules*

The following selection will be performed:

- Medical history finding: not ongoing at informed consent (MH.MHENRPT is ‘BEFORE’)
- Concomitant disease finding: still ongoing at informed consent (MH.MHENRPT is ‘ONGOING’ or missing)

5.4.3 *Presentation of results*

Medical history and concomitant diseases will be tabulated separately by treatment and overall. Each table will show:

- The number and percentage of subjects with findings
- The number and percentage of subjects with findings by system organ class and preferred term

	Statistical Analysis Plan	
CLI-10067AA1-01	Final Analysis	Final 1.0 of 30MAY2024

All medical history and concomitant diseases data will be listed separately.

5.5 PROCEDURES AND MEDICATIONS

5.5.1 *Available data*

All procedures are coded into system organ classes and preferred terms using the medical dictionary for regulatory activities (MedDRA, see section 10.3). For each procedure, start and stop dates or ongoing flag are collected.

All medications are coded using WHODrug (see section 10.3). ATC coding up to level 5 is available in the clinical database. For each medication, a start date(time) or prior flag and stop date(time) or ongoing flag are collected.

5.5.2 *Derivation rules*

Based on their start and stop date(time), procedures and medications will be allocated to each phase during which they were performed/administered. A procedure/medication can therefore be reported in more than one phase.

Phases are defined in section 6.2.1. Procedures/medications with (partially) missing date(time)s will be allocated to each phase unless the available parts of the procedure/medication start or stop date(time) provide evidence that the procedure/medication was not performed/taken during that phase.

Based on their start and stop date(time) procedures and medications will be allocated to one of the following categories:

- Prior: the procedure/medication stopped prior to first study treatment administration
- Maintained: the procedure/medication started before first study treatment administration and was ongoing at first study treatment administration
- Concomitant: the procedure/medication started at or after first study treatment administration

For procedures/medications with (partially) missing date(time)s not allowing allocation to one unique category, a worst-case allocation will be done based on the available parts of the medication/procedure start or stop date(time). The medication/procedure will be allocated to the first category allowed by the available data, according to the following order:

- Concomitant
- Maintained
- Prior

Note: these procedures/medications will only be allocated to the phases that match the worst-case allocated category.

5.5.3 *Presentation of results*

Procedures:

The number and percentage of subjects with procedures and the number and percentage of subjects with procedures by system organ class and preferred term

	Statistical Analysis Plan	
CLI-10067AA1-01	Final Analysis	Final 1.0 of 30MAY2024

alphabetically sorted will be tabulated per category (prior, maintained, and concomitant); by treatment and overall. Blank system organ classes and preferred terms, if any, will be shown as 'Not Available' in the tables.

Subjects having more than one procedure allocated to the same category within the same treatment, system organ class and preferred term will be counted only once.

All procedures data will be listed.

Medications:

The number and percentage of subjects with medications and the number and percentage of subjects with medications by anatomical main group (level 1), therapeutic subgroup (level 2), chemical subgroup (level 4), and preferred name will be tabulated per category (prior, maintained, and concomitant); by treatment and overall. Blank ATC levels and preferred names, if any, will be shown as 'Not Available' in the tables.

Subjects having more than one medication allocated to the same category within the same treatment, anatomical main group, therapeutic subgroup, chemical subgroup, and preferred name will be counted only once.

All medications data will be listed.

5.6 EXPOSURE TO STUDY TREATMENT

5.6.1 *Available data*

For each study treatment administration, the start and end date(time)s, kit number, the dose, the infusion rate, the reason for interruption or rate change and the action taken during the infusion will be recorded.

5.6.2 *Presentation of results*

All exposure data will be listed.

6. GENERAL METHODOLOGY

6.1 ANALYSIS SETS

6.1.1 *Analysis sets*

The following analysis sets will be considered in the statistical analysis:

Enrolled Set (ENR): subjects who *signed an informed consent* to participate in this study

Randomised Set (RND): subjects who were *randomised* into this study

Safety Set (SAF): all randomised subjects who receive a dose of study treatment, including partial dose

PK Set: all subjects from the safety set excluding subjects without any valid PK measurement or with important protocol deviations significantly affecting PK, for example, use of non-permitted medications.

Notes:

- Having signed an informed consent is defined as having a complete informed consent signature date in the database.
- Randomised is defined as having a randomisation date in the database or any information to confirm randomisation.
- Having received at least one dose of study treatment is defined as having an exposure date or any information confirming exposure.
- Exact definition of important protocol deviations significantly affecting PK evaluations will be discussed by the Chiesi team during the Data Review Meeting (DRM) and described in the DRR and/or PK DRR. The PK set will be defined in the DRR and/or PK DRR. See section 6.1.3.1 for further details. Subjects will not be excluded on the basis of statistical analysis or for PK reasons, except in the cases defined in the European Medicine Agency guideline on the Investigation of Bioequivalence

Unless stated otherwise, the SAF will be used for the general characteristics, demographics and baseline characteristics, immunogenicity and safety tables and figures and the RND will be used for the general characteristics and safety listings. In addition, the PK set will be used for demographics and baseline characteristics tables, if different than the SAF. PK set will be used for the PK tables, listings and figures.

6.1.2 *As planned versus as actual analysis*

For the safety, immunogenicity, other variables (TG2) and PK analyses the actual treatment of the subject will be considered. The general characteristics analyses will be by planned treatment. In the listings the actual treatment will be presented.

6.1.3 *Exclusion of data from the statistical analyses*

The important/non-important protocol deviation definitions are defined in the Protocol Deviation Criteria List and will be used to identify cases that will be

discussed by Chiesi during the DRM. Decisions on whether subjects are to be excluded from the analysis set and/or values are to be excluded from the analysis will be fully documented in the DRR and/or PK DRR.

In case of important protocol deviations impacting specific time points, only the affected data at the specific time point will be excluded from the applicable analysis sets. These cases will be documented in the DRR and/or PK DRR.

6.1.3.1 EXCLUSION OF DATA FROM PK ANALYSIS

Subjects and/or PK data can be excluded from the PK set or PK analysis based on the important protocol deviations with potential impact on PK. Below, the rules for handling PK assessments not performed, or performed out of the allowed window, or not reportable are described. In addition to the important protocol deviations, PK data can be excluded based on specific rules after disclosure of the bioanalytical data or specific criteria for PK parameters. The criteria of the latter are described in section 2.1.2.

Important protocol deviations

The impact of PK assessments not performed, or performed out of the allowed window, or not reportable will depend on the number of deviations per profile and the timing of the deviation:

At predose

The impact of serum PK assessments performed out of allowed window or taken after start of infusion will be evaluated during the DRM.

For serum PK assessments not performed or not reportable at pre-dose, see section 6.3.1 for proper imputation rules for PK parameter estimation.

At t_{max}

For serum PK assessments not performed, or performed out of allowed window, or not reportable at the expected t_{max} , the general rule is the following: the resulting estimation of C_{max} , t_{max} and AUCs could not be accurately determined, and these parameters will be excluded from PK analyses. This deviation will have no impact on the estimation of $t_{1/2}$. The expected t_{max} of CHF10067 is within 1 hour from the end of infusion.

At t_{inf}

[figure not shown]
For serum PK assessments not performed, or performed out of allowed window, or not reportable at the expected t_{inf} , the general rule is the following: the resulting estimation of C_{inf} could not be accurately determined, and this parameters will be excluded from PK analyses. This deviation will have no impact on the estimation of $t_{1/2}$.

At last planned sampling time point

For serum PK assessments performed out of allowed window at the last planned sampling time point, in order to minimise the risk to under- or overestimate AUC_{0-t} , AUC_{0-t} will be calculated using the theoretical time of the last planned timepoint instead of the actual time. Note that in case the last sample is taken before the planned sampling time point, this AUC_{0-t} can only be estimated if λz is reliably measurable.

		Statistical Analysis Plan	
CLI-10067AA1-01	Final Analysis	Final 1.0 of 30MAY2024	

For serum PK assessments not performed or not reportable at the last planned sampling time point, the following schema will be used to determine the handling of impacted AUCs (C_x , C_y and C_z are adjacent concentration samples at the end of the profile, with $t_x < t_y < t_z$; thus t_z being the last planned sampling time point of the profile):

Multiple missing PK assessments

The impact of multiple PK assessments not performed or not reportable, i.e., at least 2 adjacent intermediate values are missing, or more than 3 intermediate values are missing, the PK profiles will be discussed case by case in the DRR and/or PK DRR. If 1, or 2 non adjacent intermediate values are missing, no impact on PK parameter estimation is expected.

Two serum samples at the same actual time

The Phoenix WNL software cannot handle two identical actual sampling time points in a profile. Therefore, if two serum samples are taken at the same time, the sample taken closest to the planned sampling time point will be used while the other will be excluded from PK parameter estimation.

Rules after disclosure of the bioanalytical data

After disclosure of the bioanalytical data, subjects and/or PK data will not be excluded based on post-hoc statistical analysis or for pharmacokinetic reasons, except for certain cases described below (in line with the EMA guideline on the investigation of bioequivalence CPMP/EWP/QWP/1401/98 Rev.1 2010).

All BLQ values

When plasma concentrations are BLQ at all time points, no PK parameters will be estimated and the subject will be excluded from the PK set.

Non-zero baseline concentration > 5% of C_{max}

Statistical Analysis Plan

CLI-10067AA1-01

Final Analysis

Final 1.0 of 30MAY2024

Subjects with Day 1 pre-dose values exceeding 5% of the C_{max} will be excluded from the PK set.

AUC_{0-t} lower than 5% of the corresponding geometric mean AUC_{0-t}

Subjects with an AUC_{0-t} lower than 5% of the corresponding geometric mean AUC_{0-t} (calculated without inclusion of data from the outlying subject) will be excluded from the PK set.

Abnormal PK concentrations or profiles

Abnormal PK concentrations or profiles will be discussed case by case in the PK DRR.

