7.2.1.2 Determination of CHF10067

Blood samples (1 sample = 3.5 mL) for determination of serum CHF10067 will be collected at the following timepoints: pre-dose (within 75 minutes from start of infusion), at the end of infusion, 2, 4, 8, and 20 hours after the end of infusion and 5, 7, 14, 28, 56, and 84 days post-dose. The selected timepoints are based on the results obtained after single dose in healthy subjects. Timepoints may be adjusted during the study if the PK profile in IPF patients is significantly different than healthy subjects. In that case, decisions will be taken by the Safety Advisory Committee and appropriately documented. The total number of timepoints is not expected to be modified.

The time deviation window for PK sampling will be:

- \pm 5 minutes for timepoints \leq 2 hours
- \pm 15 minutes for timepoints $>$ 2 hours and \leq 8 hours
- \pm 1 hour for the timepoint of 20 hours
- \pm 1 day for Days 5 and 7
- \pm 2 days for Days 14, 28, 56, and 84.

The processing, storage and shipment of samples are detailed in the Laboratory Manual document.

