2. PHARMACOKINETIC, AND IMMUNOGENICITY ANALYSES

2.1 PHARMACOKINETIC ANALYSES

2.1.1 Available data

Blood samples will be collected for the determination of CHF10067 in serum at the following time points: pre-dose (within 75 minutes from start of infusion), at the end of infusion, and 2, 4, 8, and 20 hours after the end of the infusion and 5, 7, 14, 28, 56 and 84 days post-dose.

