2.1.2 Endpoints and derivation rules

The following PK parameters will be derived for serum CHF10067:

- AUC_{0-t} , AUC_{inf} , C_{max} , t_{max} , C_{inf} , t_{inf} , CL , V_z , $t_{1/2}$.

Standard non-compartmental methods will be used for the calculation of the PK parameters from the individual serum concentration – time profiles using actual sampling time points from start of infusion. If actual sampling time is not available, nominal time will be used (see also section 6.1.3.1). The analysis will consider time only in hours and minutes. Any seconds in the time part of a record will be imputed by zero. The area under the serum concentration-time curve (AUC) will be calculated according to the linear trapezoidal method.

PK parameters definition

- AUC_{0-t} : AUC from 0 to the last quantifiable concentration;
- AUC_{inf} : AUC from 0 to infinite time calculated as: AUC extrapolated to infinity will be calculated as the sum of AUC_{0-t} and a residual part extrapolated to infinite time. The residual area from the last concentration data point to infinite time is calculated using the approximation:

$$\int_t^{\infty} C_t dt = C_t / \lambda_z$$

where λ_z is the first order terminal rate constant, estimated by linear regression of the terminal loglinear segment of the plasma log concentration curve, and C_t is the last quantifiable concentration data point;

- C_{max} and t_{max} : the value and time of the maximum serum concentration will be obtained directly from the experimental data without interpolation;
- C_{inf} and t_{inf} : the value and time of the serum concentration at end of infusion;
- CL : clearance will be calculated as:

$$Dose / AUC_{inf}$$

- V_z : volume of distribution will be calculated as:

$$Dose / (\lambda_z * AUC_{inf})$$

	Statistical Analysis Plan	
CLI-10067AA1-01	Final Analysis	Final 1.0 of 30MAY2024

- $t_{1/2}$: terminal half-life, associated with negative slope ($-\lambda z$), will be calculated as $0.693/\lambda z$ from the individual drug concentration time profiles

Criteria for $t_{1/2}$ estimation

- At least three time points (excluding t_{max}) should be used for the determination of the elimination rate constant (λz), otherwise the $t_{1/2}$ as well as the derived parameters (AUC_{inf} , CL and Vz) cannot be estimated and will be presented as “NE” (not estimated) in the tables.

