6.2.4 Analysis visits

The analysis will use the visits indicated on the subject's eCRF, while for the time points related to the PK concentration data and the vital signs and oxygen saturation assessments a windowing approach will be used (see time window definitions below). For PK parameter calculation the actual sampling time will be considered, as reported in section 2.1.2.

The screening value is the last available and non-missing value before Day 1. This value corresponds to the screening visit, except in case of retesting. Reason for this approach is the use of retest results for subject eligibility assessment.

Unscheduled assessments will not be used in the analysis unless it is selected as screening value, or per time window definitions below.

The unscheduled assessments will be checked during the data review meeting before database lock, and any different approach to the rule defined above will be documented in the data review report.

Baseline is defined in section 6.2.2.

All scheduled and unscheduled assessments will be listed.

Statistical Analysis Plan

CLI-10067AA1-01

Final Analysis

Final 1.0 of 30MAY2024

Except when defined by time windows, the analysis visit labels will be assigned using the following rules:

- All planned screening, re-screening, eligibility recheck, etc. visits occurred during the screening phase will be presented as 'Screening'.
- All planned visits occurred during a scheduled day, will be presented as 'Day x' (x = study day, e.g. 'Day -1', 'Day 1', etc.)
- Early termination visits will be presented as 'Early Termination'
- Unscheduled visits will be presented as 'Unscheduled' unless the decision to reallocate the visit is fully documented in the DRR. In case of reallocation, the unscheduled visit will be presented with the same label as the replaced planned visit (see rules above)
- Other visits not covered by the rules above will be presented using similar labels to the ones used in SDTM (XX.VISIT)

For PK data, AVISIT(N) will be assigned per PK profile of interest and will be based on the eCRF visit of the corresponding study treatment administration.

The analysis time point labels for pharmacokinetic concentration data, vital signs and oxygen saturation, will be assigned using the following time windowing rules.

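### SAP 6.1.3.1 drops a subject's AUCs when the end-of-infusion sample is missing or off-window, although losing that sample changes AUC by only a few per cent

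*SAP*

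**What the plan says.** SAP 6.1.3.1, under the paragraph on tmax, covers a sample at the expected tmax that was not taken, was taken outside its window or gave no reportable result. As a general rule, Cmax, tmax and "AUCs could not be accurately determined, and these parameters will be excluded from PK analyses". The expected tmax "of CHF10067 is within 1 hour from the end of infusion".

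The SAP does not name the sample, but the schedule in SAP 2.1.1 leaves only one candidate. After the pre-dose sample, blood is drawn "at the end of infusion, and 2, 4, 8, and 20 hours after the end of the infusion", so end of infusion (EOI) is the only planned time inside that hour. Protocol 7.2.1.2 sets the window at plus or minus "5 minutes for timepoints" up to 2 hours.

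Other rules bear on the same point:

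- The tinf paragraph of SAP 6.1.3.1 concerns the same EOI sample and removes only Cinf, which "could not be accurately determined, and this parameters will be excluded from PK analyses".
- For a last sample outside its window, AUC0-t is kept and "will be calculated using the theoretical time of the last planned timepoint instead of the actual time".
- One missing intermediate sample is taken to have no effect on the PK parameters (SAP 6.1.3.1, multiple missing assessments).
- SAP 6.1.3 says that a deviation at a specific time point removes only the affected data at that time point.
- PK parameters are computed "using actual sampling time points from start of infusion" (SAP 2.1.2), and SAP 6.2.4 repeats this: "For PK parameter calculation the actual sampling time will be considered".

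**The concern.** Cmax and tmax depend directly on the sample at the peak. AUC does not: it accumulates over 12 weeks, and one early point carries little of it. The off-window case is the weaker part of the rule, because actual times are used and a mistimed sample is placed where it was drawn. As written, an EOI sample drawn 6 minutes late removes every AUC for that subject by default.

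AUC0-t and AUCinf serve the secondary PK objective and two of the three power models in SAP 2.1.3, with six active subjects per dose. The rule is also silent on CL and Vz. Both are computed from AUCinf (SAP 2.1.2), and the SAP names both when AUCinf is excluded for excessive extrapolation.

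The gentler handling of other deviations does not contradict the tmax rule. It shows that the SAP elsewhere matches the response to the size of the effect.

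**Working it through.** The plan gives no figure for the effect of losing this sample, so there is none to reproduce.

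**Exact loss.** Write Ce for the EOI concentration, C2 for the concentration 2 h later and T for infusion duration in hours, with a pre-dose value of 0 and the linear trapezoidal rule of SAP 2.1.2. Over the interval from 0 to T + 2:

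- with EOI: 0.5·T·Ce + (Ce + C2)
- without EOI: 0.5·(T + 2)·C2
- difference: **Ce × 1 h + (T/2) × (Ce − C2)**

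This is algebra and holds for any PK model. Only its share of AUC needs assumptions. Roughly, peak ≈ dose/V1 and AUC ≈ dose/CL, so the share is near (CL/V1) × 1 h. With CL 0.2 L/day and V1 3 L that is 0.2/(3 × 24) = 0.28%.

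**Assumed inputs (none are in the documents).**

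- Samples at 0, EOI, EOI + 2, 4, 8 and 20 h, then 4, 6, 13, 27, 55 and 83 days after start. Quantification limit 0.1 mg/L; λz from the last three quantifiable points.
- Main grid, 1400 profiles: linear one or two compartments, CL 0.1–1.5 L/day, V1 2.5–5 L, T 0.5–5.5 h. The upper T follows the vital-sign windows in SAP 6.2.4.
- Stress grid, 5940 profiles: adds CL to 2.5 L/day, V1 from 2 L, fast distribution and T to 6 h.

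| Result | Main grid | Stress grid |
|---|---|---|
| EOI missing, AUC0-t | −0.10 to −2.38% (median −0.56%) | −0.10 to −5.45% (median −0.96%) |
| Same, half-life ≥ 10 days, worst | −0.67% | −1.12% |
| Loss in hours of peak concentration | 1.00–1.25 | 1.00–1.96 |
| EOI missing, CL and Vz, largest rise | +2.43% | +5.76% |
| EOI missing, observed Cmax, worst | −9.4% | −38.1% |
| EOI 6 min late, AUC0-t, worst | −0.12% | −0.33% |
| EOI 6 min early, AUC0-t, worst | −0.42% | −0.95% |
| EOI 60 min late, AUC0-t, worst | −1.2% | −3.0% |

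Further checks:

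- Nonlinear elimination (288 profiles): AUC0-t falls by 0.18 to 4.76%.
- A differently chosen linear grid (CL 0.1–1.2 L/day, V1 2.5–4 L): 0.14 to 1.87%, and up to 4.5% with CL raised to 3 L/day.
- Profiles whose last quantifiable sample is as early as Day 5: up to 2.7%.
- With EOI present, the linear trapezoidal rule over the sparse late samples already overstates AUC0-t by about 1.5 to 17% in the non-stress scenarios, which is more than losing EOI takes away.

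**Effect on dose proportionality.** For log doses 0, 0.693 and 1.099 with six subjects each, the mean is 0.597 and Sxx = 3.703. The 90% CI half-width is t(0.95, n−2)·σ/√Sxx, with σ = √ln(1 + CV²). At an assumed CV of 30%, σ = 0.2936, and 1.746 × 0.2936/1.924 = 0.266.

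| Assumed CV | All 18 | One subject excluded (depends on dose) |
|---|---|---|
| 20% | 0.180 | 0.181–0.190 |
| 30% | 0.266 | 0.268–0.282 |
| 50% | 0.429 | 0.431–0.454 |

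Keeping one AUC that is low by a fraction b shifts the slope by (x − x̄)/Sxx × ln(1 − b). The shift is largest at 1000 mg:

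- b = 0.024: (0.597/3.703) × 0.0243 = 0.004, and the six-subject geometric mean falls by 0.4%.
- b = 0.055: 0.009, and the geometric mean falls by 0.9%.

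Even if all six 3000 mg subjects lost the sample, the slope would shift by −0.020 at b = 0.024 (−0.046 at 0.055). Excluding all six would leave only two dose levels.

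**How often.** If 2, 5 or 10% of active subjects had such a deviation (assumed), the chance of at least one among 18 is 1 − (1 − p)^18 = 30, 60 or 85%.

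**The case against.** The strongest case is that the practical cost is small and the rule is not absolute. It is called a general rule. Exclusions are decided and documented in the data review report, and SAP 2.1.2 and 2.1.4 provide for excluded parameters to be marked, footnoted and listed. Excluding one subject widens the slope interval by about 1 to 6% (0.266 to 0.268–0.282). Protocol 7.2 gives PK sampling priority, so the deviation should be uncommon. The study is descriptive, without a power calculation, and AUC is a secondary variable. Infusion details and earlier PK are redacted, so no range for the bias can be fixed from the documents, and some checks exceed 2.4%.

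Much of this stands: the gain is modest and conditional, and the percentages rest on assumptions. It does not rescue the default. A footnoted or listed AUC is still out of the summaries and the power model. Discretion at data review leaves the written rule in place, and the SAP 6.1.3 statement that only affected data are removed points towards keeping AUC. The upper figures (4.8% nonlinear, 5.5% stress) come from unfavourable assumed settings and remain small beside the error the trapezoidal method already carries. Late samples were run to 60 minutes, and their loss stayed well below that of a missing sample.

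**Conclusion.** The concern holds. The tmax rule removes AUC for a deviation that, under assumed antibody-like PK, lowers AUC0-t by about 0.1 to 2.4%. The loss is at most 0.7% on the main grid when the half-life is 10 days or more, and 5.5% at worst in the stress grid. For an EOI sample a few minutes off-window and used at its actual time, the effect is below 1% in every linear setting run. The identity for the loss is exact; its size as a percentage depends on the assumed clearance, volume and infusion time.

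The exclusion of Cmax and tmax when EOI is missing should stay, since observed Cmax can fall by 9% (38% under stress). This is a cheap improvement that should be made. Nothing here shows that a study conclusion would change.

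**What to change.** In SAP 6.1.3.1, limit the tmax rule to Cmax and tmax, leave Cinf under the tinf rule, and add:

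> *A missing, mistimed or non-reportable end-of-infusion sample alone does not exclude AUC0-t, AUCinf, CL or Vz. These are computed from the available samples at actual times, remain subject to the criteria in section 2.1.2, and are footnoted.*

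This also closes the gap on CL and Vz. The cost is SAP wording and a table footnote. The price is a small downward bias in a retained AUC and a small upward bias in CL and Vz: about 0.1 to 2.4% on the main assumed grid, and up to about 5.5 to 6% in the stress case.
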